### **5.2.1 Dosage Form**

The lyophilized, sterile finished product contains romidepsin, 10 mg/vial and 20 mg/single use vial Povidone, USP, and hydrochloric acid to adjust pH. Romidepsin (for infusion) is supplied in a dual-pack configuration with a single use diluent for romidepsin vial that contains 2 mL of 80% Propylene Glycol, USP, and 20% Dehydrated Alcohol (ethanol), USP; sterile for use in reconstitution of romidepsin (for Infusion).

### **5.2.2 Storage and Handling**

The dual pack is to be stored at 20 to 25°C (68 to 77°F), excursions permitted between 15 to 30°C (59 to 86°F) [USP controlled room temperature]. Romidepsin (for infusion) is stable for at least 36 months at 25°C/60% relative humidity (RH) as well as for 6 months at 40°C/75% RH and is stable against heat (for 3 months at 50°C) and humidity (for 3 months at 25°C/83% RH). Appropriately trained personnel using aseptic technique should reconstitute the drug. A volume of 2 mL of reconstitution diluent is added to the lyophilized powder and swirled until contents of the vial are free from visible particles. The reconstituted product stock solution at 5 mg/mL is chemically stable for at least 8 hours at room temperature. However, whenever possible, drug should be prepared within 4 hours of dose administration. A volume of the 5 mg/mL stock solution containing the appropriate dose for the patient will be diluted in 0.9% Sodium Chloride Injection, USP (0.9% saline) for intravenous infusion, as directed by the protocol. This dilution should result in a final drug concentration within the demonstrated stability range of 0.02 to 0.16 mg/mL for reconstituted romidepsin, that is compatible with polyvinyl chloride (PVC), ethylene vinyl acetate (EVA), and polyethylene (PE) intravenous infusion bags; glass bottles may also be used. The romidepsin infusion solution is chemically stable for at least 24 hours at room temperature. However, whenever possible, drug should be prepared within 4 hours of dose administration.

### **Supplier(s)**

Celgene Corporation will supply ISTODAX® (romidepsin) to study participants at no charge.

### **5.2.3 DRUGS DISPENSATION AND ACCOUNTABILITY**

The clinical trial supplies of romidepsin will be provided in a dual pack containing one vial of romidepsin for injection and one vial of diluent. The drug vial will contain a lyophilized powder of 10 mg of lyophilized romidepsin and 20 mg of povidone, USP (used as a bulking agent). The diluent vial will contain 2 mL of a 4:1 mixture of propylene glycol and ethanol. Appropriately trained personnel using an aseptic technique should reconstitute the drug. A volume of 2 mL of diluent should be added to the lyophilized powder and swirled until contents of the vial are free from visible particles. This provides a stock solution at 5 mg/mL. The stock solution will be diluted using aseptic technique in 500 mL 0.9% Sodium Chloride Injection, USP (0.9% saline) for patients with a body surface area (BSA) ranging from 1.35 to 2.79 m^2 and in 1000 mL 0.9% saline for patients with a BSA of 2.8 m^2. Reconstituted drug in saline is compatible with PVC, EVA, and PE IV infusion bags as well as glass bottles. The vials containing the investigational product and the kits they are packaged in will be labeled according to the Good Manufacturing Practice guidelines and the local requirements

#### **Special Handling Instructions**

Females of childbearing potential should not handle or administer romidepsin unless they are wearing gloves.

#### **Record of Administration**

Accurate records will be kept in the source documents of all drug administration (including prescribing and dosing).

## **6.0 CRITERIA FOR SUBJECT ELIGIBILITY.**

### **6.1 Subject Inclusion Criteria**

1. Pathology confirmed lymphoma or multiple myeloma.
  - Hodgkin lymphoma is eligible for either phase and will be considered a B-cell lymphoma in the phase IIa study.
  - Phase IIa portion, subjects must have B-cell lymphoma, T-cell lymphoma, or multiple myeloma.
2. Relapse or progression after at least 1 systemic therapy.
3. Measurable disease for phase IIa portion only.

- Lymphoma (includes CTCL patients who are NED in skin): CT or PET/CT by modified Cheson criteria with incorporation of PET.
  - Multiple myeloma: Patient must have measurable disease and therefore must have at least one of the following:
    - i. Serum M-protein  $\geq 0.5\text{gm/dL}$  ( $\geq 5\text{gm/L}$ )
    - ii. Urine M-protein  $\geq 200\text{mg/24hr}$
    - iii. Serum FLC assay: involved FLC  $\geq 10\text{mg/dL}$  ( $\geq 100\text{mg/L}$ ) provided serum FLC ratio is abnormal.
  - CTCL: mSWAT  $>0$ , or absolute Sezary count  $\geq 1000\text{ cells}/\mu\text{L}$ .
4. Age  $\geq 18$  years at the time of signing the informed consent form.
  5. Able to adhere to the study visit schedule and other protocol requirements.
  6. Previous systemic anti-cancer therapy must have been discontinued at least 3 weeks prior to treatment in this study. If there is progression of disease on that therapy and all adverse effects have resolved to Grade 1 or baseline, in which case 2 weeks is acceptable.
  7. Previous radiation, hormonal therapy, and surgery must have been discontinued or completed at least 2 weeks prior to treatment in this study and adverse effects must have resolved. Lymph node or other diagnostic biopsy within 2 weeks is not considered exclusionary.
  8. Short course systemic corticosteroids for disease control, improvement of performance status or non-cancer indication (< 7 days) must have been discontinued at least 7 days prior to study treatment. Stable ongoing corticosteroid use ( $\geq 30$  days) up to an equivalent dose of 15 mg of prednisone is permissible.
  9. ECOG performance status of  $\leq 2$  at study entry (see Appendix A).
10. Laboratory test results within these ranges:
- Absolute neutrophil count  $\geq 1.0/\text{mm}^3$ .
  - Platelet count  $\geq 70\text{ K}/\mu\text{L}$ , if thrombocytopenia is due to bone marrow involvement platelet count must be  $\geq 50\text{ K}/\mu\text{L}$ .
  - Renal function assessed by calculated creatinine clearance as follows (see Appendix B):
    - Phase Ib subjects must have calculated creatinine clearance  $\geq 50\text{ml/min}$  by Cockcroft-Gault formula.

- Phase IIa subjects must have calculated creatinine clearance  $\geq$  30ml/min by Cockcroft-Gault formula. See section below, "Dosing Regimen", regarding lenalidomide dose adjustment for calculated creatinine clearance  $<$  60ml/min and  $\geq$  30ml/min.
  - Total bilirubin  $\leq$  1.5 x upper limit of normal (ULN); 3 x ULN if due to hepatic involvement.
  - AST (SGOT) and ALT (SGPT)  $\leq$  3 x ULN; 5 x ULN if due to hepatic involvement.
11. All study participants must be registered into the mandatory Revlimid REMS® program, and be willing and able to comply with the requirements of the REMS® program.
12. Females of reproductive potential must adhere to the scheduled pregnancy testing as required in the Revlimid REMS® program. Men must agree to use a latex condom during sexual contact with a FCBP even if they have had a successful vasectomy. See Appendix C: Risks of Fetal Exposure, Pregnancy Testing Guidelines and Acceptable Birth Control Methods.

† A female of childbearing potential is a sexually mature female who: 1) has not undergone a hysterectomy or bilateral oophorectomy; or 2) has not been naturally postmenopausal for at least 24 consecutive months (i.e., has had menses at any time in the preceding 24 consecutive months).

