## 4.0 OVERVIEW OF STUDY DESIGN/INTERVENTION

### 4.1 Design

**Phase Ib:** The phase Ib portion of the study is designed to determine the MTD of romidepsin and lenalidomide. All patients must have a relapsed or refractory B-cell lymphoma, T-cell lymphoma, or multiple myeloma. Patients will be treated on a 28-day cycle with romidepsin infused on day 1, 8, and 15, and lenalidomide taken orally on days 1-21. The design is a standard 3+3 dose escalation (Table 1) of romidepsin and lenalidomide. The first cohort will enter at dose level 1.

Dose Level	Romidepsin	Lenalidomide
-1	8 mg/m 	10 mg
1	8 mg/m 	15 mg
2	8 mg/m 	25 mg
3	10 mg/m 	25 mg
4	14 mg/m 	25 mg

Table 1: Description of dose level

DLT is defined in cycle 1 (in phase Ib).

Definitions:

- Grade  $\geq$  3 non-hematologic (attributed to study drugs)
- Grade 4 hematologic toxicities (attributed to study drugs) defined as:
  - Grade 4 thrombocytopenia (platelets  $< 25$  K/ $\mu$ L)
  - Grade 4 neutropenia (absolute neutrophil count (ANC)  $< 0.5$ )
- Grade 3 thrombocytopenia or neutropenia that results in a  $> 3$  day delay in any romidepsin dose in cycle 1.
- One week or greater delay in initiating cycle 2 day 1 due to continued drug-related toxicity.

Any patient with an adverse event that meets the DLT definition is considered evaluable for MTD determination. Patients who do not have a DLT, but received  $<3$  doses of romidepsin or  $<80\%$  (17/21) of the doses of lenalidomide during cycle 1 will not be evaluable for MTD and will be replaced.

Three patients will be initially treated in each cohort until the MTD is determined. If dose level 4 (full dose of each drug) is achieved without DLT after 1 cycle that dose level will be deemed the optimal dose and the study will proceed to a phase IIa expansion cohort. Patients treated at MTD in the phase Ib portion will be counted towards the phase IIa accrual by disease subtype and also for all efficacy and toxicity endpoints unless they did not have measurable disease at point of study entry as allowed in the phase Ib portion.

**Phase IIa:** The phase IIa portion will further assess the toxicity and safety and allow a preliminary assessment of the efficacy of the combination to provide background for a potential future subtype specific phase II study (see Section14.0).

DLT is defined in cycles 1-4 (in phase IIa)

Definitions:

- Grade  $\geq$  3 non-hematologic (attributed to study drugs)

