## **9.7 Dose Continuation, Modification and Interruption**

Subjects will be evaluated for AEs at each visit with the NCI CTCAE v4.0 (Appendix H): NCI CTCAE v4.0) used as a guide for the grading of severity. DLTs as defined will be tabulated in cycle 1 of the phase Ia and cycles 1-4 of the phase IIa portion of the study. The toxicity decision rule for the IIa portion is described in Section 14.0. The sections below describe dose reduction steps, instructions for initiation of a new cycle of therapy and dose modifications during a cycle of therapy. Inability to meet treatment criteria will result in holding the dose.

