**TABLE 5: Dose Modifications for Lenalidomide and Romidepsin**

NCI CTC Toxicity Grade	Dose Modification Instructions (also see Instructions for Initiation of a New Cycle above)
Grade 3 neutropenia not associated with fever	
 
• Hold lenalidomide and romidepsin dose.
 
• Follow CBC at least weekly.
 
• Upon recovery to grade <math>\leq</math> 2 resume romidepsin and lenalidomide at one dose reduction.
 
• Omitted doses are not made up (Romidepsin doses may be given up to 3 days late).
 

Grade 3 neutropenia associated with fever (temperature <math>\geq 38.5^{\circ}</math> C) or Grade 4 neutropenia	
 
• Hold lenalidomide and romidepsin dose.
 
• Follow CBC at least weekly.
 
• Upon recovery to <math>\leq</math> grade 2 resume lenalidomide and romidepsin at next lower dose level.
 
• Omitted doses are not made up. (Romidepsin doses may be given up to 3 days late)
 

Thrombocytopenia <math>\geq</math>Grade 3 (platelet count <math>< 50,000/\text{mm}^3</math>)	
 
• Hold lenalidomide and romidepsin dose.
 
• Follow CBC at least weekly.
 
• Upon recovery to <math>\leq</math> grade 2 resume lenalidomide and romidepsin at next lower dose level.
 
• Omitted doses are not made up. (Romidepsin doses may be given up to 3 days late)
 

Non-blistering rash	
Grade 3	
 
• If Grade 3, hold lenalidomide dose. Follow at least weekly.
 
• If the toxicity resolves to grade 1, resume lenalidomide at next lower dose level.
 
• Omitted doses are not made up.
 

Grade 4	
 
• If Grade 4, discontinue lenalidomide. Remove patient from study.
 

Desquamating (blistering) rash- any Grade	
 
• Discontinue lenalidomide. Remove patient from study.
 

Neuropathy	
Grade 3	
 
• If Grade 3, hold lenalidomide dose. Follow at least weekly.
 
• If the toxicity resolves to grade 1 resume lenalidomide at next lower dose level.
 
• Omitted doses are not made up.
 

Grade 4	
 
• If Grade 4, discontinue lenalidomide. Remove patient from study.
 

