## **10.0 EVALUATION DURING TREATMENT/INTERVENTION**

### **10.1 A new cycle of treatment may begin on the scheduled Day 1 of a new cycle if:**

- ANC is  $\geq 1.0$  K/ $\mu$ L
- Platelet count is  $\geq 70$  K/ $\mu$ L or within 10 K/ $\mu$ L of baseline.
- Serum creatinine concentration  $\leq 2.0 \times$  ULN or  $\leq$  baseline
- AST (SGOT) and ALT (SGPT)  $\leq 2.0 \times$  ULN or  $\leq 3.0 \times$  ULN in presence of demonstrable liver metastases.
- Serum potassium and magnesium are within normal range.
  - In cycle 2 and beyond in Phase Ib and any cycle in Phase IIa, magnesium and potassium levels may be checked up to 3 days prior to administration of romidepsin. If levels are within range at that time point romidepsin may be administered without recheck unless clinically indicated (such as vomiting, diarrhea, or initiation of medications that may affect electrolytes).
  - Supplements must be given to patients whose potassium and/or magnesium are below normal range.
    - Magnesium supplementation: If levels are below normal range, but  $\geq 1.2$  mg/dL, patients can receive at least 2gm magnesium IV and proceed to treatment without re-checking labs. Patients can be treated if magnesium levels are above normal range.
    - Potassium supplementation: If levels are below normal range, but  $\geq 3.2$  mEq/L, patients can receive at least 20mEq potassium IV and proceed to treatment without re-checking labs.
- Any drug-related maculo-papular rash or neuropathy that may have occurred has resolved to  $\leq$  grade 1 severity
- Any other clinically significant adverse events that may have occurred have resolved to  $\leq$  grade 2 severity.

**If these conditions are not met on Day 1 of a new cycle, the subject will be evaluated weekly and a new cycle of treatment will not be initiated until the toxicity has resolved as described above.**

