## **15.0 RESEARCH PARTICIPANT REGISTRATION AND RANDOMIZATION PROCEDURES**

### **15.1 Research Participant Registration**

Confirm eligibility as defined in the section entitled Criteria for Patient/Subject Eligibility.

Obtain informed consent, by following procedures defined in section entitled Informed Consent Procedures.

During the registration process registering individuals will be required to complete a protocol specific Eligibility Checklist.

All participants must be registered through the Protocol Participant Registration (PPR) Office at Memorial Sloan-Kettering Cancer Center. PPR is available Monday through Friday from 8:30am – 5:30pm at [contact]. Registrations must be submitted via the PPR Electronic Registration System (<http://ppr/>). The completed signature page of the written consent/RA or verbal script/RA, a completed Eligibility Checklist and other relevant documents must be uploaded via the PPR Electronic Registration System.

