### **17.4 Communication of DLTs**

For the purposes of this clinical trial, A DLT is defined as non-hematologic toxicity of grade  $\geq 3$  (attributed to study drug) and hematologic grade 4 (attributed to study drug) toxicity defined as grade 4 thrombocytopenia of any duration, failure of recovery of absolute neutrophil count  $\geq 1.0$  K/ $\mu$ L or platelets to  $\geq 50$  K/ $\mu$ L within 14 days of last treatment; or inability to receive day 1 of cycle 2 due to continued drug-related toxicity from the cycle. During the course of the Phase Ib portion of this study, all DLTs that occur will be immediately communicated via email to each participating site/investigator. Additionally, routine conference calls will be conducted with all participating sites to communicate all safety issues including DLTs. The frequency of these conference calls will be determined by enrollment rate of the trial. Lastly, all events that qualify as SAEs should be reported according to the protocol guidelines.

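### Inclusion criterion 10 prints the neutrophil limit as 1.0/mm³, a thousand times below the 1.0 K/µL that the protocol uses for dosing and recovery

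*Combined protocol and SAP*

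**What the plan says.** The first laboratory bullet of inclusion criterion 10 (Section 6.1) reads "Absolute neutrophil count $\geq 1.0/\text{mm}^3". The bullet after it gives the platelet limit in thousands per microlitre: "Platelet count $\geq 70\text{ K}/\mu\text{L".

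The same number appears with a different unit in three other places:

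- Section 10.1, to start a new cycle: "ANC is $\geq 1.0$ K/ $\mu$ L".
- Section 10.2, before each romidepsin dose other than day 1 of a cycle: the same 1.0 K/µL limit.
- Section 17.4, in the description of a dose-limiting toxicity (DLT): "failure of recovery of absolute neutrophil count $\geq 1.0$ K/ $\mu$ L".

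Section 15.1 makes Section 6 the standard for registration: "Confirm eligibility as defined in the section entitled Criteria for Patient/Subject Eligibility". Section 9.7 covers patients who miss the dosing limits: "Inability to meet treatment criteria will result in holding the dose".

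**The concern.** An eligibility threshold is an operative rule. Sites complete a checklist against it and submit laboratory source documents, the coordinating centre reviews them, and Section 16.3 requires IRB approval in advance for any departure that involves eligibility. A limit of 1 cell/µL would exclude almost nobody. As printed, a patient with marked neutropenia qualifies, and registering that patient would not count as a deviation.

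The likely cost is modest: a patient could be registered and then held on day 1. The protection against worse is the day 1 dosing limit, and only Section 10.1 supplies it, because Section 10.2 leaves out day 1 of each cycle. Section 10.1 is worded for a new cycle. That it also covers cycle 1 has to be inferred, chiefly from a sub-item on electrolyte timing that refers to every phase IIa cycle. The inference is reasonable, but an entry limit should not depend on it.

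**Working it through.** No figure in the plan has to be reproduced, because the limit is a stated threshold. The check is a unit conversion followed by a look at how the protocol uses the unit elsewhere.

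**Conversion.** 1 mm³ = 1 µL, and K denotes 1000.

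| Place | Limit as printed | Cells per µL |
|---|---|---|
| Section 6.1, inclusion 10 | 1.0/mm³ | 1 |
| Section 10.1 | 1.0 K/µL | 1.0 × 1000 = 1000 |
| Section 10.2 | 1.0 K/µL | 1000 |
| Section 17.4 | 1.0 K/µL | 1000 |

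Ratio: 1000 / 1 = 1000.

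**Comparison with grade 4.** Section 4.1 gives "Grade 4 neutropenia (absolute neutrophil count (ANC) $< 0.5" with no unit. Assuming K/µL, that is 0.5 × 1000 = 500 cells/µL, and 500 / 1 = 500. On that assumption the printed entry limit is 500-fold below the grade 4 cut-off.

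**Worked patient.** Take an ANC of 0.4 K/µL, which is 0.4 × 1000 = 400/mm³.

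- Inclusion 10 as printed: 400 ≥ 1.0, so the patient is eligible.
- Sections 10.1 and 10.2: 0.4 < 1.0, so the patient cannot be dosed.
- Section 4.1, with the K/µL assumption: 0.4 < 0.5, so the value is in the grade 4 range.

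**Could /mm³ mean thousands per mm³ here?** Table 5 uses the same unit for platelets: "platelet count < 50,000/\text{mm}^3". Dividing, 50,000 / 1000 = 50 K/µL, which equals the platelet limit in Section 10.2. In that instance /mm³ goes with the full count. Section 6.1 itself writes platelets with a K and gives the Sézary count in full as 1000 cells/µL. Nothing in the document supports an implied thousand.

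**Is it corrected elsewhere?** Section 8.2 requires a blood count within 14 days of starting treatment but gives no threshold. No other section restates the neutrophil entry limit.

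**The case against.** The strongest reply is that nobody would be misled. A floor of 1 cell/µL makes no clinical sense, the number 1.0 matches the dosing limits, and a haematologist would supply the missing thousand. Several safeguards follow: central review of laboratory documents for participating sites (Section 15.1.1), a blood count within 14 days of treatment (Section 8.2), hematology on cycle 1 day 1 (Table 7), and the dosing limits themselves. This stands, and it is why the point is minor. It does not make the printed limit correct.

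Second, entry and dosing limits need not agree. Platelets are 70 K/µL at entry (50 with marrow involvement), 70 K/µL or within 10 of baseline for a new cycle, and 50 K/µL within a cycle. That is fair: the other sections show the intended unit but do not prove that the entry value had to be 1.0 K/µL. Still, a real difference between the two limits would not be a factor of 1000.

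Third, the document's count notation is loose. The neutropenia DLT limit carries no unit, and the evidence on how /mm³ is used comes from one platelet entry in Table 5. This weakens the argument from usage a little. The literal meaning of the unit does not depend on it.

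Fourth, a multiplier might have been lost when the PDF was read. This cannot be fully excluded, but the expression shows no gap and the adjacent platelet bullet kept its K.

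**Conclusion.** The concern holds: the neutrophil limit in inclusion 10 is wrong as written, by a factor of 1000 (1 cell/µL against 1000 cells/µL). The evident intent is 1.0 K/µL. This rests on the text having been read correctly from the PDF; the comparison with grade 4 also assumes that the unlabelled 0.5 is in K/µL.

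It is a minor point, worth correcting. It has no effect on the sample size, the phase IIa dose-reduction rule or any planned analysis. It should not be presented as inflating DLT counts either, because a hematologic grade 4 event counts as a DLT only when attributed to study drugs. What remains is an entry criterion that would admit patients the protocol does not intend to treat.

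**What to change.** In Section 6.1, inclusion criterion 10, change the bullet to ANC ≥ 1.0 K/µL (1000/mm³). The eligibility checklist is not part of the documents, so confirm that it carries the same limit. As optional tidying, add K/µL to the 0.5 neutrophil limit in the phase Ib and phase IIa DLT definitions in Section 4.1.

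The cost is one unit in one bullet. Nothing in the design or the analysis changes.

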#### **Metabolism and Excretion:**

The metabolic profile of lenalidomide in humans has not been studied. In healthy volunteers, approximately two-thirds of lenalidomide is eliminated unchanged through urinary excretion. The process exceeds the glomerular filtration rate and therefore is partially or entirely active. Half-life of elimination is approximately 3 hours.

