**\*1 cycle equals 28 days**

### **9.3 Treatment Plan romidepsin/lenalidomide Phase IIa**

The entire accrual is planned to have up to 51 patients in the phase IIa portion; each disease cohort will have 15 patients (B-cell lymphoma, multiple myeloma or PTCL). There will be an expansion of the T-cell cohort to include an additional 6 patients with acute T-cell leukemia/lymphoma. After a sufficient number of patients have been enrolled for determination of the primary and secondary objectives, cohorts may be closed to accrual by the MSK principal investigator. The MTD for lymphoma has been determined to be 14mg/m^2 romidepsin on Days 1, 8, 15 and 25mg lenalidomide from Days 1-21. The patients treated at MTD in the phase Ib cohort (if measurable disease at enrollment) and phase IIa cohort will be evaluated both collectively and by disease subtype. Patients with more than one histology are eligible and will be assigned by the principal investigator to a specific disease subtype.

- In patients with MM, due to the presence of toxicities, patients will be dosed at romidepsin 10mg/m^2 and lenalidomide 25mg (see table 2a). If two of six (or fewer) patients treated at this dose level develop dose-limiting toxicities, the initial dosing for subsequent patients will be decreased to romidepsin

10mg/m^2 and lenalidomide 15mg. For example, if two of four patients treated at this initial dose develop dose-limiting toxicities, the starting dose for subsequent patients will be reduced as above.

- At a starting dose of romidepsin 10mg/m^2 and lenalidomide 15mg, should 2 of 6 (or less) patient will be reduced to romidepsin 8mg/m^2 and lenalidomide 15mg.
- At a starting dose of romidepsin 8mg/m^2 and lenalidomide 15mg, should 2 of 6 (or less) patients have dose-limiting toxicities, the initial dose for subsequent patients will be reduced to romidepsin 8mg/m^2 and lenalidomide 10mg.

Table 2a: Multiple Myeloma Dosing for Phase IIa Portion

Dose level	Romidepsin	Lenalidomide
1	10	25
-1	10	15
-2	8	15
-3	8	10

The treatment plan for the phase IIa portion is described below:

Romidepsin/Lenalidomide Cycle 1 Day 1 + subsequent Cycle X

Romidepsin MTD IVPB over 4 hours

Lenalidomide MTD PO q days 1-21

Romidepsin/Lenalidomide Cycle 1 Day 8

Romidepsin MTD IVPB over 4 hours

Romidepsin/Lenalidomide Cycle 1 Day 15

Romidepsin MTD IVPB over 4 hours

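### Phase IIa admits patients with creatinine clearance of 30–59 mL/min and promises a lenalidomide adjustment for them, but the protocol contains none, and Section 9.3 sets starting doses by disease only

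*Combined protocol and SAP*

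**What the plan says.** Section 6.1 (laboratory criteria) sets renal eligibility by phase. For the first phase, "Phase Ib subjects must have calculated creatinine clearance" of at least 50 mL/min. For the second, "Phase IIa subjects must have calculated creatinine clearance" of at least 30 mL/min. The phase IIa item then refers to a section below, named Dosing Regimen, "regarding lenalidomide dose adjustment for calculated creatinine clearance" under 60 and at or above 30 mL/min.

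Starting doses for phase IIa appear in two places:

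- Section 4.2 carries the phase Ib MTD forward as the phase IIa dose.
- Section 9.3 states: "The MTD for lymphoma has been determined to be" romidepsin 14 mg/m² with lenalidomide 25 mg on days 1–21. Myeloma patients start at romidepsin 10 mg/m² with lenalidomide 25 mg. Table 2a gives three lower myeloma starting levels (10/15, 8/15 and 8/10), reached through DLT counts.

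On elimination, Section 5.1.2 reports that in healthy volunteers "approximately two-thirds of lenalidomide is eliminated unchanged through urinary excretion". Section 11.5 adds that the drug may remain in semen longer when kidney function is not normal.

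**The concern.** The eligibility criterion opens phase IIa to patients with reduced clearance on the footing that their lenalidomide will be adjusted. If the adjustment rule is absent, an explicitly eligible group has no determinable protocol dose for a drug whose elimination, on the protocol's own account, is largely renal. That is first a patient-safety matter.

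It also reaches the primary endpoint. Section 14 monitors DLTs over cycles 1–4 and lowers the dose for later patients when counts reach 8 of the first 15 or 16 of the first 30. Those counts are read as evidence about the MTD. A patient with clearance of 30–59 mL/min might enter them at 25 mg or at some other dose, and Section 14 does not say how either case counts.

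**Working it through.** No sample size, power or error rate underlies this point, so the check is textual.

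**1. Is there a Dosing Regimen section?** It is not in the table of contents, and no heading in the body carries that name. Section 9 is numbered 9.1 to 9.9 without a gap, so nothing suggests a lost subsection. The figure at the end of Section 4.1 could not be checked, but it stands before Section 6.1, and the reference points forward.

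**2. Does any other text supply the adjustment?**

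- Section 4.1, Table 1, and Section 9.2, Table 2: phase Ib dose levels, with no renal condition.
- Section 4.2: the MTD is used in phase IIa, with no renal condition.
- Section 5.1.3 (Prescribing Information): supply and REMS registration only.
- Section 9.3 and Table 2a: doses by disease and by DLT count.
- Section 9.4: timing, missed doses and the diary.
- Section 9.7, Tables 3–6: reduction steps and toxicity or cardiac triggers, with no row for clearance.
- Section 10.1: a serum creatinine limit for beginning a new cycle, which is not a starting-dose rule.
- Table 7: the visit schedule.
- Appendix B: the Cockcroft-Gault formula alone.

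None ties a lenalidomide dose to clearance.

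**3. Setting the sections side by side, by clearance band.**

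| Clearance (mL/min) | Eligible, phase Ib | Eligible, phase IIa | Adjustment announced in 6.1 for phase IIa | Initial lenalidomide in 9.3 |
|---|---|---|---|---|
| 60 or more | yes | yes | no | 25 mg |
| 50–59 | yes | yes | yes | 25 mg |
| 30–49 | no | yes | yes | 25 mg |

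The last column is the same in every row, for lymphoma and for myeloma at its first level. In the lower two rows it does not reflect the adjustment that Section 6.1 announces.

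**4. What differs between the two lower bands.** At 30–49 mL/min, phase Ib could contribute no patients, so the MTD carries no data for them. At 50–59 mL/min, phase Ib patients were eligible and Table 1 set their dose without adjustment, whereas Section 6.1 announces one for phase IIa. Sections 4.1 and 14 pool phase Ib MTD patients who have measurable disease with phase IIa. The pooled set could therefore hold patients from the same clearance band started under different rules.

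**5. What a site can do.** A site that adjusts has no protocol figure to use, and Section 16.3 requires prospective IRB approval for treatment changes the protocol does not allow. A site that does not adjust sets Section 6.1 aside. The oral overdose definition in Section 17.2 is measured against the protocol-specified dose, which is unclear for these patients. Section 7.0 names four recruiting institutions, so practice may diverge.

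**6. Weight in the analysis.** Section 14 counts 15 + 8 + 15 + 6 = 44 patients at the MTD. One patient is 1/44 = 2.3% of that set and 1/15 = 6.7% of the first look. This is the weight of any patient; it does not estimate an effect of renal function.

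**The case against.** Several stronger readings are tempting, and the documents do not support them.

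- *A reader might infer that Section 9.3 gives one starting dose to everyone.* It does not. It gives two disease-specific combinations and the lower Table 2a levels. Only the initial lenalidomide component is common, and what matters is that none of it varies with clearance.
- *A reader might infer that the protocol orders the full dose for these patients.* Section 6.1 expressly says an adjustment applies. A site reading the whole protocol meets a promised instruction that is missing, alongside starting-dose rules that ignore it. Uncertain and inconsistent dosing is the supportable consequence.
- *A reader might infer that the whole 30–59 band lies outside the MTD evidence.* Only 30–49 mL/min does.
- *A reader might infer that the DLT rate is biased.* The number of affected patients is not given, and no change in the chance of reaching 8 of 15 can be derived. Bias is possible but has not been shown.
- *A reader might want the MTD set limited to patients who started at the full MTD.* Phase IIa myeloma patients start below the lymphoma MTD by design, yet Section 14 counts 8 myeloma patients among the approximately 44 and groups the disease subtypes together. That restriction could remove up to 8 of 44 for a reason unrelated to renal function.

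It is also fair that DLT monitoring through cycle 4, the toxicity reductions in Section 9.7 and the creatinine limit in Section 10.1 still operate. They act after treatment has begun or between cycles, and they limit harm without supplying a starting dose. The elimination figure comes from healthy volunteers. None of this restores the missing rule.

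**Conclusion.** The point holds in this form: Section 6.1 relies on a section and an adjustment that the protocol does not contain, and Sections 4.2 and 9.3 set starting doses without regard to clearance. The dose for an eligible phase IIa patient with clearance of 30–59 mL/min cannot be determined consistently. For those at 30–49 mL/min, phase Ib offers no supporting experience.

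The correction is needed because the gap bears on the dose of the first such patient enrolled, however few there turn out to be. The statistical consequence is an undefined rule for how these patients count in the DLT monitoring; its numerical effect is unknown. The conclusion assumes that the figure not available for checking holds no renal dosing rule, and that no separate dosing document governs the trial. The protocol cites none for this purpose.

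**What to change.** **Dosing text.** The sponsor should reconcile Sections 6.1, 9.3 and 4.2 so that eligibility and treatment sections agree on how phase IIa patients with clearance of 30–59 mL/min are started, and should correct or remove the dead cross-reference. Which rule applies is for the sponsor to decide; none is proposed here.

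**Section 14.** Add a statement of whether a patient whose starting lenalidomide dose differs because of renal function counts in the phase IIa DLT rule. Add a separate tabulation of DLTs for patients with clearance below 60 mL/min. Word the addition so that the phase IIa myeloma cohort stays in the pooled set.

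**Cost.** Amendment wording, a short addition to Section 14 and one extra table. Clearance is already calculated for eligibility, so no new baseline measurement is needed, and the sample size does not change.
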